## 1.0 SUMMARY OF STUDY

The present study proposes to study the effect of a single preoperative dose of baclofen on pain treated in the first 24 hours after kidney stone-related surgeries using a placebo-controlled, double-blind methodology. Because this patient population often has a history of significant opioid use, which would be expected to alter postoperative pain medication requirements, patients will be stratified into those which would be expected to be opioid tolerant (use >30 OME daily) and those who are generally opioid naïve.

## 2.0 BACKGROUND & RATIONALE

Postoperative pain continues to be a significant clinical problem. Use of perioperative adjuvants has improved postoperative pain control. The GABA-B receptor agonist, baclofen, is an appropriate drug to trial as such an analgesic adjuvant. Support for this assertion is given below

**Baclofen pharmacology.** The drug baclofen (chemical name) is a GABA derivative. Its mechanisms of action is through the metabotropic GABA-B receptor and is G-protein linked to potassium channels leading to neuronal hyperpolarization. Baclofen is a white powder, practically odorless powder which is manufactured in 10 and 20 mg tablets with typical doses for spasticity of 10-20 TID. It is rapidly absorbed and has half-life of 2-4 hours. 85% of the compound is excreted unchanged in urine.

Sites of action are peripheral, spinal and supraspinal. Selective spinal infusion is utilized to control spasticity. Notable for this discussion, CASL imaging of the brain before and after 21 days of baclofen treatment (20 QID) demonstrated reduced rCBF in the ventral striatum and medial prefrontal cortex and increased rCBF in the lateral OFC, (a region involved in suppressing previously rewarded behavior) and cerebellum. rCBF was also blunted in the insula bilaterally [Franklin et al, 2011].

**Baclofen produces analgesia.** Baclofen produces analgesia by itself as measured in rats and mice in the hot plate, tail flick and acetic acid-induced writhing [Aley and Kulkarni, 1989, 1991; Balerio and Rubio; mult other] In rats with chronically inflamed paws baclofen increased Substance P release raising issues related to acute vs. chronic analgesic benefits of the GABA-B agonists [Malcangio and Bowery, 1994; Galeotti et al 1996]. Baclofen produced analgesia in primates in the formalin test [Sharma et al, 1993]. In chemotherapy-induced neuropathic pain models baclofen produced significant but erratic analgesia [Xiao et al, 2008]. Intrathecal nociceptin antagonized baclofen-induced analgesia in a mouse tail flick assay [Citterio et al, 2000] and baclofen-induced analgesia was absent in GIRK2 knockout mice [Blednov et al] Baclofen administered spinally (intrathecally) produces analgesia in rat thermal pain models that can be antagonized by GABA-B antagonists [Aran and Hammond ]. Whitehead et al [2012] demonstrated peripheral analgesic effects of baclofen in a mouse arthritis model.

Baclofen's analgesic effects may be acting via the same mechanism by which heterosegmental noxious stimuli produce inhibition (nociceptive inhibition) since such inhibition has been demonstrated to act via GABA-B and mu opioid mechanisms [Tambell et al, 2009]. Consistent with this, analgesia produced by 100 Hz electroacupuncture as involves GABA-B mechanisms [Silva et al]. GABA-B receptor blockade also blocks foot-shock induced "stress-induced" analgesia, but not forced swim stress or psychological stress [Tokuyama et al] although others have observed potentiation of forced swim stress-induced analgesia by baclofen [Houston et al, 1997]. In the spinal substantia gelatinosa activation of GABA-B receptors presynaptically block neurotransmitter release [Yang and Ma] and NK1 receptor expression [Enna et al]. Other sites of action related to pain include the rostral agranular insular cortex [Jasmin et al] and lateral preoptic area [Lim et al]. The supraspinal analgesic effects of baclofen appear to act via adrenergic and opioidergic spinal mechanisms [Jasmin et al; Ignatov and Andreev;] with potentially a cholinergic and GABA-A portion to contribution [Tamayo et al 1988; Zarridast MR and Djavdan M].

In humans, baclofen has had a particular role as an anesthetic for cranial nerve-related neuropathic pains such as trigeminal neuralgia [Knotkova and Pappagallo] . Early anecdotal reports (e.g. Harmer and Larson) suggested it worked for postherpetic neuralgia in facial distributions but not spinal distributions [Terrence et al, 1985]. In humans, the spinal administration of baclofen has also demonstrated short-term analgesic effects on spinal cord injury-related pain and post-stroke pain [Taira et al, 1995]. One presumed mechanism for the action of baclofen on facial pain is the presence of GABA-B receptors on

trigeminal primary afferent neurons whose activation leads to a potentiation of voltage-dependent potassium currents. Baclofen has demonstrated analgesic effects on surgical pain in females [Corli et al]

**Baclofen interacts with opioids synergistically.** Gordon et al (1995) observed potentiation of morphine analgesia on post-operative pain but not of pentazocine-induced (kappa) analgesia. Panerai et al [1985] had previously demonstrated baclofen prolonged the analgesic effect of fentanyl on post-operative pain. Notably, baclofen also potentiates the analgesia produced by clonidine in rat models [Przesmycki et al]

**Baclofen reduces addictive behaviors.** In a randomized, double-blind placebo-controlled clinical trial Assadi et al [2003] used baclofen for the maintenance treatment of opioid dependence. In a 12 week trial of 20 TID. Baclofen was superior over placebo in terms of opiate withdrawal syndrome and depressive symptoms. Trends towards reductions in opioid craving and self-reported opioid and alcohol use were noted but not proven.

Baclofen has also been noted to reduce cigarette consumption [Franklin et al, 2009]

Corwin et al [2012] in a double-blind, placebo-controlled, crossover study in 12 subjects demonstrated that baclofen (20 TID) reduced binge-eating. Slight but significant increases in depression symptomatology occurred. Tiredness, fatigue and upset stomach were the most commonly reported side effects.

Ling and Shoptaw [1998] in a clinical series of ten patients reported reduced cocaine-craving due to baclofen with good safety and tolerability. General reviewes posit its beneficial effects in multiple forms of addiction [Kumar et al, 2013]

The place in the treatment of addictive behaviors where baclofen treatment has found its greatest audience is in the realm of alcohol addiction [reviewe – Gorsane et al] but with mixed results for efficacy by placebo-controlled, double-blind randomized trials [e.g. Garbutt et al 2010]. Effects on alcohol craving, use and abuse have also been demonstrated with general acceptance of beneficial effects but varying levels of effect [Dore et al, 2011; Vuittonet et al 2014; Tyacke et al, 2010; Leggio et al, 2010; Johnson et al, 2005 ] – similar benefits have been noted for GABA-B positive allosteric modulators [Filip et al, 2014]

Baclofen reversed cognitive deficits induced by acute cocaine in rhesus monkeys and normalized activation of prefrontal cortex sites[Porrino et al, 2014]

In rat models, baclofen dose-dependently reduced heroin-seeking behavior [Spano et al, 2007], reversed behavioral sensitization to morphine [Bartoletti et al, 2007] and prevents heroin-induced reinstatement of heroin-seeking behaviors [Spano et al, 2007] and enhances extinction of opiate and methamphetamine-induced conditioned place preference [Heinrichs et al, 2010; Voigt et al, 2011] particularly stress-accenuated morphine-induced conditioned place preference [Meng et al, 2014]. In rodent models of cocaine- or heroin-seeking behaviors, baclofen was found to attenuate these behaviors [DiCiano and Everitt, 2003]. Similar results are noted for alcohol-seeking and drinking behavior [Maccioni and Colombo, 2009].

Baclofen reduced ethanol consumption in mice, but only in those which were phenotypically less prone to heavy drinking behaviors [Villas Boas et al, 2012]. Baclofen reduced nicotine- [Paterson et al, 2004] and morphine self-administration in rats and a GABA(B)-antagonist increased morphine administration [Ramishini et al, 2013]

Baclofen administered into the locus coeruleus attenuated morphine withdrawal signs [Riahi et al, 2009]

Presumed mechanisms for baclofen's actions on addictive behaviors is an interaction wth dopaminergic neurons of the ventral tegmental area where baclofen leads to Girk signaling [Arora et al, 2011] with a subsequent reduction in dopamine release in the nucleus accumbens.

**Baclofen toxicology and drug/drug interactions.** There have been limited toxicities or side effects of baclofen. Odd reactions include things such as the induction of hiccup-like respirations [Srivasta et al, 2014] or diabetes insipidus [Silversides and Scott] In rats, intraventricular baclofen impaired memory [Zarrindast et al, 2001] CB1 receptor antagonism decreases analgesia due to baclofen and GABA(B) antagonists reduce analgesia due to cannabinoids [Naderi et al, 2005].

Most toxicity reports relate to withdrawal [Ross et al, 2011] or excessive dosing [Roy and Wakefield, 1986; Leung et al 2006] with CNS effects predominant (loss of consciousness, delirium, hypertension). Because it is kidney-cleared, toxicity is more common in patients with advanced nephropathy [El-Husseini et al, 2011]

Some increases in depression have been noted, but in the spinal cord injury patients, use of baclofen improved psychiatric symptoms [Margetis et al, 2014]

DeFeudis [1984] suggested that GABAergic drugs might have a role in both analgesia and drug addictions, particularly related to opioids but did not go so far as to suggest co-administration.

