### **4.0 INCLUSION & EXCLUSION CRITERIA**

Inclusion criteria:

Adult patients (age  $\geq 19$  y.o.) scheduled for kidney stone-related surgery

Exclusion criteria:

[1] History of allergy to baclofen [2] Any condition which might limit appropriate report and treatment of postoperative pain (e.g., non-English speaking; severe psychiatric disease)

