#### 5.0 RANDOMIZATION/RECRUITMENT DETAILS (If applicable)

- Randomization groups, how will subjects be randomized:

All subjects who are patients of Drs. [name] and/or [name] and scheduled for kidney stone-related surgery will be potentially recruited.

Part 1: In an initial open run-in period, six patients will be recruited and given a dose of 10 mg baclofen preoperatively so that potential side effects can be assessed in an unblinded fashion.

Part 2: After that, patients will be identified and initially stratified into two groups based on preoperative opioid use. If daily using >30 Oral Morphine Equivalents (OMEs) for more than one month they will be designated as Opioid Tolerant. Otherwise, they will be included in the Opioid Naïve group. These two groups will then be each randomized (envelope assignment) into receiving either baclofen (10 mg, p.o. x 1) or placebo as a preoperative medication such that there will be 4 groups of 20 patients identified:

Group 1: Opioid Tolerant – baclofen

Group 2: Opioid Tolerant – placebo

Group 3: Opioid Naïve – baclofen

Group 4: Opioid Naïve - placebo

- Blinded  Yes  No (Single  Double  please check box).

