#### 6.0 STUDY INTERVENTIONS/PROCEDURES

- Study design: Placebo-controlled double-blind
- Comparison groups (for prospective and clinical trials only).

Placebo treated individuals

- Timeline of interventions (for prospective and clinical trials only).

Patients will be recruited preoperatively by Drs. [name] and [name], in addition to anesthesiology-related personnel in the KPAC. Informed consent will be obtained at that time. On the Day of Surgery, subjects will be contacted by study personnel in the Preoperative Holding area to confirm patient participation and then a randomization envelope containing a single dose of either baclofen or placebo will be opened (Groups 1&2 intermixed; Groups 3&4 intermixed; envelopes will be prepared ahead of time by a different investigator according to a randomization table). Subjects will then consume the pill in the envelope and this will be recorded. Patients will then be treated intraoperatively and postoperatively according to the standard of care associated with these surgeries but with an attempt to utilize consistent doses of intraoperative opioids other agents across groups and standardized PACU orders. After discharge from the

PACU patients' pain will be treated with PCA morphine. Notably, the treating anesthesiologist and all PACU personnel will be blinded to the drug that was administered preoperatively. The total use of analgesics, measures of any other side effects (nausea, excessive sedation) will be recorded for 24 hours.

- **Measured Outcomes:**
  - a. Primary outcomes: Postoperative opioid consumption (measured as OMEs)
  - b. Secondary outcomes: Incidence of nausea/vomiting; excessive sedation per patient self assessment; any other untoward events

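### Minor safety improvement: the plan's own caution about baclofen in advanced nephropathy does not reach the eligibility criteria, the pre-dose step or the precautions line

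*Combined protocol and SAP*

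**What the plan says.** All references are to the combined protocol and SAP.

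- **Section 2.0, pharmacology paragraph:** 85% of baclofen leaves unchanged by the kidney, the half-life is 2-4 h, and usual spasticity doses are 10-20 mg three times daily.
- **Section 2.0, toxicology paragraph:** "Because it is kidney-cleared, toxicity is more common in patients with advanced nephropathy". The sentence just before it begins "Most toxicity reports relate to withdrawal", adds excessive dosing, and goes on "with CNS effects predominant (loss of consciousness, delirium, hypertension".
- **Section 4.0:** any adult aged 19 or over who is booked for kidney stone-related surgery qualifies, subject to two exclusions: "1] History of allergy to baclofen [2] Any condition which might limit appropriate report and treatment of postoperative pain". The examples given for the second are language and severe psychiatric disease.
- **Section 5.0:** in the open run-in, "six patients will be recruited and given a dose of 10 mg baclofen preoperatively so that potential side effects can be assessed". In the main part, patients are randomised to "receiving either baclofen (10 mg, p.o. x 1) or placebo as a preoperative medication".
- **Section 6.0:** on the day of surgery, staff contact the patient to "confirm patient participation and then a randomization envelope containing a single dose of either baclofen or placebo will be opened", and the patient then takes the pill. After the recovery unit, "pain will be treated with PCA morphine". Side effects are recorded for 24 hours.
- **Section 8.0:** the metabolism row repeats that the kidney clears the drug. The only contraindication is allergy. The precautions row is a general statement of safety, and the only CNS side effect listed is mild sedation.

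**The concern.** The background names one group in which the study drug is more often toxic. The population has kidney stones, so renal function is an obvious eligibility question. Yet the three places where staff would meet the caution (eligibility, the step before dosing, the drug information sheet) do not carry it. A clinician may still hold back a patient with poor renal function, but the plan does not ask for that. The run-in and the 24-hour recording can pick up a side effect after dosing; they do not keep such a patient from being dosed.

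What is at stake is the safety of a small and unknown number of patients. The primary outcome, the randomisation and the planned analysis are not affected.

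**Working it through.** **Text check.** The caution was traced through each operating section.

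| Place | Renal content |
|---|---|
| 4.0 inclusion | none |
| 4.0 exclusions | none (allergy; conditions limiting pain report and treatment) |
| 5.0 run-in and randomisation | none |
| 6.0 step before dosing | none (participation is confirmed) |
| 8.0 metabolism | kidney clearance stated as a fact |
| 8.0 contraindications and precautions | none |

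This is an omission, not a contradiction: no later section denies the caution.

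**Size of the effect.** The plan has no figure of its own to reproduce, so a simple model sets the scale.

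Inputs from Section 2.0: renal share 85%, half-life 2-4 h, usual dose 10-20 mg three times daily. Input from Section 5.0: one 10 mg dose.

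Assumptions: one compartment, linear kinetics, instant and complete absorption, volume and non-renal clearance unchanged, and 85% taken as the renal share of clearance. Let k be the fraction of normal renal function. The values k = 0.25 and k = 0.10 are illustrations, because the documents do not define advanced nephropathy.

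1. Relative clearance = 0.15 + 0.85k. This is 0.3625 at k = 0.25 and 0.235 at k = 0.10.
2. Half-life multiplier = 1 / relative clearance. This is 2.76 and 4.26. Applied to 2-4 h, it gives 5.5-11.0 h and 8.5-17.0 h.
3. Peak load after one dose is 10 mg at every k, which follows directly from instant absorption. For comparison, the steady-state peak on 10 mg every 8 h at normal function is 10 / (1 - 2^(-8/half-life)): 10.7 mg with a 2 h half-life and 13.3 mg with 4 h.
4. Amount left after t hours = 10 × 2^(-t/half-life):

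| Renal function | 12 h | 24 h |
|---|---|---|
| normal | 0.2-1.3 mg | under 0.2 mg |
| 25% | 2.2-4.7 mg | 0.5-2.2 mg |
| 10% | 3.8-6.1 mg | 1.4-3.8 mg |

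5. Total exposure, as the dose that would give the same exposure at normal function, = 10 / relative clearance: 10/0.3625 = 27.6 mg and 10/0.235 = 42.6 mg. A typical day is 3 × 10 = 30 mg to 3 × 20 = 60 mg.
6. Limit of that comparison: 10 / (0.15 + 0.85k) reaches 60 mg when 0.15 + 0.85k = 1/6, that is at k of about 0.02. With no renal function it would be 10/0.15 = 66.7 mg.

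So the peak does not rise, the tail is longer, and total exposure stays at or below an ordinary day's exposure except where renal function is almost absent.

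**The case against.** The case for leaving the plan alone has substance. The dose is single and at the low end. The background ties most toxicity to withdrawal or excess dosing, and gives no dose or duration for the nephropathy statement, so the documents cannot show that it applies to one 10 mg tablet. No toxic level is given against which to judge the amounts left at 12 or 24 h. The patients' own surgeons and anaesthesiology staff recruit, and care follows usual standards, so a patient with very poor renal function might well be noticed. Consent pages are not in the public copy and might carry a warning. All of this lowers the grade. It does not remove the gap: no renal finding is linked to eligibility, and a consent warning would not be an exclusion.

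Three stronger readings are tempting, and the documents support none of them.

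- A reader might infer that loss of consciousness or delirium is to be expected in renal patients here. Those effects are listed in the sentence on withdrawal and excessive dosing, not in the nephropathy sentence.
- A reader might infer that retained baclofen would deepen sedation from PCA morphine. The background describes potentiated analgesia with opioids and shows nothing about added sedation.
- A reader might infer that dosing an affected patient is likely. In all, 6 + 20 + 20 = 46 patients get baclofen, and 1 - (1 - p)^46 is 37% at p = 1% and 99% at p = 10%. The documents give no prevalence, so these figures only restate the assumption and carry no weight.

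**Conclusion.** The omission is certain from the text. Its consequence is minor. The eligibility rule admits a group that the plan's own background flags as at higher risk, and nothing before dosing would stop such a patient. Under the stated model, that patient would have a longer exposure (half-life roughly 2.8 to 4.3 times normal at 25% and 10% of renal function) with an unchanged peak and a total within ordinary daily use.

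The size rests on the one-compartment assumptions, on the 85% share and on the illustrative renal fractions. The comparison with a spasticity regimen does not prove safety in renal patients around surgery; it only argues against a higher grade. The number of patients affected is unknown. This is a cheap safety improvement, not a flaw in the trial's inference.

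**What to change.** 1. Add a third exclusion to Section 4.0: *known advanced nephropathy, from the medical history or the latest creatinine/eGFR already on record*. Apply it once, at screening, in both the run-in and the randomised part. No new blood test and no second check at the envelope are needed.
2. The investigators should fix a numeric cut-off before enrolment. The documents give none, so any value is an assumption; an eGFR limit between 15 and 30 mL/min/1.73 m² is an example only.
3. Replace the precautions entry in Section 8.0 with: *cleared by the kidney; higher risk of toxicity in advanced nephropathy*. Leave the contraindications line as it is.

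The cost is one line in Section 4.0, one replaced line in Section 8.0 and one screening item. The eligible pool becomes slightly smaller, by an unknown amount, and the results would not apply to patients with advanced nephropathy. Because the check uses existing records, it would miss a patient with no recorded history or value. The 10 mg dose, the planned 6 + 80 patients and the analysis do not change.

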### **3.0 OBJECTIVE(S) & HYPOTHESIS**

Purpose of study:

To determine whether a single, oral dose of baclofen alters postoperative opioid requirements

Study Hypothesis:

We hypothesized that a single, oral dose of baclofen given to patients undergoing kidney stone surgery will reduce postoperative opioid requirements measured in the PACU and in the first 24 hours following surgery.

### **4.0 INCLUSION & EXCLUSION CRITERIA**

Inclusion criteria:

Adult patients (age  $\geq 19$  y.o.) scheduled for kidney stone-related surgery

Exclusion criteria:

[1] History of allergy to baclofen [2] Any condition which might limit appropriate report and treatment of postoperative pain (e.g., non-English speaking; severe psychiatric disease)

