## **9.0 STATISTICAL CONSIDERATIONS**

- Original Plan for Statistical Analysis : Data analysis will be by ANOVA analysis using Tukey's HSD for post-hoc analysis for primary outcome data and Fishers Exact test for categorical incidence data. A mid-point analysis was proposed after the study of 40 subjects.

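### Scheduled procedure is left out of both the stratification and the primary ANOVA; if the enrolled operations differ in opioid need, this costs precision but does not bias the estimate on average

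*Combined protocol and SAP*

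**What the plan says.** - **Eligibility.** Section 4.0 takes adults "scheduled for kidney stone-related surgery". No procedure is listed or excluded. Section 1.0 refers to "the first 24 hours after kidney stone-related surgeries".
- **Stratification.** In Section 5.0, "patients will be identified and initially stratified into two groups based on preoperative opioid use". That is the only factor. Each opioid stratum is then randomised to baclofen or placebo "such that there will be 4 groups of 20 patients identified".
- **Envelopes.** Section 6.0 describes one set per opioid stratum ("Groups 1&2 intermixed; Groups 3&4 intermixed"), with nothing to balance procedure.
- **Care.** Section 6.0 treats patients "according to the standard of care associated with these surgeries". It also tries to keep intraoperative dosing consistent, uses a common set of PACU orders, and puts patients on PCA morphine after the PACU.
- **Analysis.** Section 9.0 says "Data analysis will be by ANOVA analysis", followed by Tukey's HSD. It lists no factors or covariates.

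**The concern.** The primary outcome is postoperative opioid consumption, so the operation is a plausible predictor of it. The scheduled operation is also known before allocation for every patient, because it is what makes the patient eligible. Section 1.0 already applies this reasoning to opioid history: the protocol stratifies on it because it is expected to change analgesic requirements. Scheduled procedure may be a second baseline factor of the same kind, and the plan does not use it.

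If procedures do differ in opioid need, the variation between them falls into the error term, and the drug comparison is less precise than it could be with the same 80 patients. The plan states no power, effect size or SD, so no stated margin exists to absorb the loss. A term added after unblinding would be open to challenge, so it has to be written down beforehand.

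**Working it through.** **The plan's own figure.** 4 groups × 20 = 80 randomised. This gives 20 v 20 within an opioid stratum, 40 v 40 for a drug main effect, and 80 − 4 = 76 residual degrees of freedom for a four-group ANOVA. The plan gives no alpha, power, effect size or SD, so the sample size cannot be reproduced further.

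**Assumptions, none of them in the documents.** Two procedure classes. A share p = 0.3 to 0.5 of patients in one class, the same in both opioid strata. A difference D between classes in OMEs, in units of the within-class SD, equal in all four groups. Two-sided alpha 0.05 and 80% power for the adjusted analysis.

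**Step 1: loss of precision.** Without the term, the error variance in within-class units is 1 + p(1−p)D². Adjustment is therefore worth p(1−p)D² more patients. At D = 1.0 that is 0.3 × 0.7 × 1 = 0.21, or 0.5 × 0.5 × 1 = 0.25. A contrast with 80% power under adjustment has power Φ(2.802/√(1 + p(1−p)D²) − 1.960) without it. In each cell, p = 0.3 comes first and p = 0.5 second:

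| D | Extra patients, p(1−p)D² | Residual SD multiplied by | Power without the term |
|---|---|---|---|
| 0.5 | 5.25%, 6.25% | 1.026, 1.031 | 78.0%, 77.6% |
| 1.0 | 21%, 25% | 1.100, 1.118 | 72.1%, 70.7% |
| 1.5 | 47.25%, 56.25% | 1.213, 1.250 | 63.6%, 61.1% |

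**Step 2: chance imbalance.** The exact probability, from two independent binomials, that the arms differ by 20 percentage points or more in procedure share:

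- 40 v 40 (8 patients or more): 6.7% at p = 0.3 and 9.3% at p = 0.5.
- 20 v 20 (4 patients or more): 22.6% and 26.8%.

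An imbalance of exactly 20 points moves the unadjusted contrast by 0.2 × D: 0.10, 0.20 and 0.30 SD for D = 0.5, 1.0 and 1.5. For scale, the difference detectable with 80% power is about 0.63 SD at 40 v 40 and 0.91 SD at 20 v 20.

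**Step 3: bias and type I error.** A 2×2 ANOVA was simulated with normal errors, 20 per cell and 20,000 runs per scenario, at D = 0.5, 1 and 2 and p = 0.3 and 0.5. Results for the drug main effect:

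- Overall type I error without the term was 0.048-0.052, and mean bias was within 0.003 SD of zero.
- With a true effect of 0.634 SD, power with the term was 0.79-0.80 at every D. Without it, power was 0.77-0.78, 0.70-0.72 and 0.51-0.54 for D = 0.5, 1 and 2.
- In null trials with an imbalance of 20 points or more, the unadjusted test rejected in about 7%, 13% and 27% of runs for D = 0.5, 1 and 2. The adjusted test stayed near 5%.

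**Step 4: cost of a needless term.** If procedures do not differ, the standard error without the term is √(2/40) = 0.2236 SD. The simulated mean standard error with the term was 0.224 SD.

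**The case against.** The strongest reply is that no document says procedure affects opioid use. No mix and no figures by procedure are given. The plural in Section 1.0 may simply mean many patients' operations, and Section 3.0 uses the singular. Section 6.0 gives PCA morphine after the PACU with no exception by procedure, and has common PACU orders and attempted consistency in intraoperative dosing. Section 5.0 limits recruitment to the patients of two clinicians. All this may mean a narrow case mix and a small D. It stands as a limit on size: at D = 0.5 the loss is about two points of power. It does not remove the point, because no section restricts the procedures.

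A reader might infer that pooling procedures biases the drug effect or inflates the false-positive rate. The plan does not support that. Allocation is random within opioid stratum, so the unadjusted estimate is unbiased on average and overall type I error holds, as Step 3 shows. The shift is conditional on the imbalance that a particular trial happens to draw.

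A reader might also apply the 23-27% imbalance risk to the trial's main question. The hypothesis in Section 3.0 concerns patients having kidney stone surgery as a whole. That is a 40 v 40 comparison, for which the risk is 7-9%. The larger figure belongs to contrasts within one opioid stratum. These still matter, because Section 9.0 plans Tukey comparisons and Section 5.0 defines four groups.

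Finally, Section 9.0 lists no factors at all, so the missing procedure term is an omission and not a stated exclusion.

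**Conclusion.** The point holds as a matter of precision. Eligibility is open to any kidney stone-related operation, and scheduled procedure appears in neither the stratification nor the stated analysis. The planned analysis remains valid; it may be less efficient than it need be. The size runs from minor (5-6% of patients at D = 0.5) to material (21-25% at 1.0 and 47-56% at 1.5). It rests on an assumed two-class mix of 30-50% and an assumed D. The documents cannot say where in that range the trial lies, and the shared postoperative regimen in Section 6.0 may push it toward the lower end. Because the term costs almost nothing when procedures are alike, prespecifying it is worthwhile across the whole range.

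**What to change.** In Section 9.0, specify the primary model as drug, opioid stratum and scheduled procedure class. Define a small number of classes, take them from the operative booking, and fix them before unblinding. Use the scheduled procedure and not the one performed, so that the variable stays a baseline one. Drop the term only if a single class is enrolled. If the four-group comparisons are kept, add the same term to that model.

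The cost is one recorded variable, a sentence in Section 9.0, and one degree of freedom per extra class (76 to 75 with two classes in the four-group model). The loss of precision is negligible if procedures do not differ. Enrolment, allocation and care are unchanged. Making procedure a further stratification factor is not needed, and with 80 patients it would risk sparse strata unless the classes were very few.
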